10 DATA HANDLING AND MANAGEMENT

Hard copy consent forms and questionnaires will be completed on site at ADUs. CRN researchers will return hard copy data directly to their CRN office and store in locked filing cabinets between regular visits from UCL researchers, whereupon the hard copy data will be taken to UCL. Questionnaires will be identified by an ID number, and participant identifiers will be kept in a separate document in a locked filing cabinet in a locked storage room in the Division of Psychiatry at UCL. The participant identifier document will be kept in a separate filing cabinet to the questionnaires.

If the questionnaire is completed over the phone, the consent process will be audio recorded using a Dictaphone. Recordings will be transferred to secure UCL servers immediately after the interview and the Dictaphones subsequently wiped of recordings. All electronic data will be stored on secure UCL systems.

11 Workpackage 2.2 – Qualitative Study

12 OBJECTIVES

In this stage of the AD-CARE study, we aim to:

- 1. Explore the views of service users, carers and practitioners regarding the strengths and weaknesses of ADUs and their component interventions
- 2. Explore service user, carer, and practitioner views concerning the role of ADUs in the acute care pathway
- 3. Integrate these findings with those from WP2.1 to generate theory around how outcomes are achieved
- 4. Develop a set of recommendations outlining best practice in this field

13 STUDY DESIGN

This will be a qualitative study. Five ADUs will be identified from the national survey carried out in WP1. At each site five service users, three carers, and three members of staff will be interviewed. The sample will be purposively sampled, based on those willing to participate in the interview process.

14 STUDY SCHEDULE

Service users: We will interview five service users from the WP2.1 cohort in each case study site, assuming 5 sites, or 25 people in total. During WP2 baseline data collection participants will be asked if they would be interested in taking part in an interview with a peer researcher about their experiences. Interview participants will be purposively sampled from those who have expressed an interest and sampling will be carried out that ensures diversity in terms of gender, ethnicity, diagnosis, satisfaction with ADU and site. We do not seek representation of views but maximum diversity among participants based upon key characteristics. Interviews will take place up to one month after the service user has been discharged from the ADU, to allow enough time for reflection, but close enough to the point of discharge that there will not be any difficulty recalling experiences of the service.

Carers: We will interview three carers of people accessing ADUs in each case study site (n= 15) recruited through convenience sampling. Service users will need to give permission for

the research team to approach their carer. When permission is granted the unit staff will approach the carer and those interested will be asked to either contact the research team themselves, or give permission for the research team to contact them. These interviews will seek to explore carers' own experiences of ADUs and the potential benefits to them, and so we will not be recruiting service user-carer pairs. Interviews will occur post discharge but the timing post discharge will be more variable and up to 6 months. We want to encourage reflection and gain a perspective on the role of the ADU in context to other supports and provision.

If service users or carers report any untoward feedback, the researcher conducting the interview will confirm with the participant whether or not they would like the researcher to pass this on to the service or other relevant person. If the untoward feedback is of a nature that leads the researcher to be concerned for the safety of others, the participant will be informed that the feedback will be passed on to the relevant service or person to be addressed, but that if desired and possible they will remain anonymous.

Staff: We will interview three members of staff working within ADUs in each case study site (n= 15). We will aim to interview a sample of staff from a broad range of disciplines (e.g. lead psychiatrist, team leader, recovery worker, peer supporter, psychologist), representative of the team structures identified during WP1 mapping. Interviews will occur at any point during the WP2 data collection period.

While many people find talking about their experiences to be helpful, some people may find that the interview brings up issues that cause emotional distress. In this case the researcher conducting the interview will provide immediate emotional support to the participant, offer to pause or postpone the interview, and, if the participant asks, will contact a person of the participant's choice (e.g. current care coordinator, carer, friend, family member, colleague) for them.

Typically, interviews will take place in a room booked by the researcher at the site the participant has previously used (as a service user, carer, or staff member). All interviews will take place in person, at a time and place mutually agreed by the participant and the researcher to ensure the location is easy to travel to, provides privacy, and is safe and comfortable. Any participant travel costs will be reimbursed, or paid for in advance. Researchers will adhere to local lone-working procedures (e.g. 'checking-in' phone calls upon completion of the interview). All service user interviews will be conducted by a peer researcher (someone with lived experience of using mental health services). Carer and staff interviews are likely to be conducted by the peer researcher, but may be conducted by other study researchers in the event that the peer researcher is unavailable.

If any participant wishes to withdraw at any point they are free to do so without any detriment to their current or future care. Unless participants inform researchers that they do not want their data used, any data collected before withdrawal will be used.

The study will be completed by 30/06/2019, with the recruitment of 25 service user participants, 15 carer participants, and 15 staff participants.

15 CONSENT

As noted above, the consent process and interviews will be conducted by study researchers. Initially, ADU staff will screen all service users consecutively admitted to their service from the start date of the study. All service users who meet the inclusion criteria will be approached by ADU staff and asked if they are willing to be contacted by researchers to discuss participation further (except at sites where service users have already given consent to be contacted directly about research projects: in this circumstance, researchers will contact service users directly once their eligibility and any risk-related safety requirements have been established). The researchers will keep a record of potential participants to be contacted and the date and the name of the clinician with whom this was agreed. Researchers will ask the clinician who spoke to each service user to note the patient's agreement to be contacted by a researcher in their patient records. Those who agree will be contacted by a researcher with an information sheet and offer to answer any questions. Potential participants will be given at least 24 hours to consider whether they would like to take part, and then if still interested a time and place will be agreed for the interview, and researchers will consent the participant before starting the interview.

In order to include those whose first language is not English, any local provision by NHS Trusts for translators will be used. However, where there are no translators provided locally it will not be possible to include non-English-speaking participants.

16 ELIGIBILITY CRITERIA

16.1 Inclusion Criteria

Inclusion criteria are as follows:

- 18 years old or older
- Have used the ADU for at least one week
- Can read and understand English (or there are translation services in place to enable communication)
- Have capacity to provide informed consent
- Do not pose too high a risk to others or themselves to participate

16.2 Exclusion Criteria

We will exclude patients who are too unwell to consent, but otherwise aim to be inclusive to gain a fully representative sample, including using local interpretation facilities when necessary.

17 RECRUITMENT

As noted above, study researchers will recruit participants. At baseline, ADU staff will screen all service users consecutively admitted to their service from the start date. All service users who meet the inclusion criteria will be approached by ADU staff and asked if they are willing to be contacted by researchers to discuss participation further (except at sites where service users have already given consent to be contacted directly about research projects: in this circumstance, researchers will contact service users directly once their eligibility and any risk-related safety requirements have been established). The researchers will keep a record of potential participants to be contacted and the date and the name of the clinician with whom this was agreed. Researchers will ask the clinician who spoke to each service user to note the patient's agreement to be contacted by a researcher in their patient records. Those who agree will be contacted by a researcher with an information sheet and offer to answer any questions. Potential participants will be given at least 24 hours to consider whether they would like to take part, and then if still interested they will be consented by a researcher, who will also collect the baseline data. Participants will be offered £20 in cash as a thank you for taking part. If participants decline this money it will be returned to the study.

While many people find talking about their experiences to be helpful, some people may find that completing the questionnaire brings up issues that cause emotional distress. In this case the researcher will provide immediate emotional support to the participant, offer to pause or postpone the interview, and, if the participant asks, will contact a person of the participant's choice (e.g. current care coordinator, carer, friend, family member, colleague) for them.

If service users or carers report any untoward feedback, the researcher conducting the interview will confirm with the participant whether or not they would like the researcher to pass this on to the service or other relevant person. If the untoward feedback is of a nature that leads the researcher to be concerned for the safety of others, the participant will be informed that the feedback will be passed on to the relevant service or person to be addressed, but that if desired and possible they will remain anonymous.

18 ANALYSIS METHODS

The interviews will be analysed by the peer researcher, directly supervised by the study qualitative leads, with input and support from the SURG and the wider research team. We will use thematic analysis and will elicit detailed descriptions of the perceived strengths and weaknesses of ADUs to inform the development of best practice recommendations, and will aim to generate theory around the processes through which ADUs might impact on recovery, as well as the outcomes measured during WP2. The qualitative data analysis software NVivo will be used to assist the management of data and facilitate systematic examination of the interview transcripts.

19 DATA HANDLING AND MANAGEMENT

Hard copy consent forms will be completed at the interview. Interviews will be recorded on Dictaphones, transferred to secure UCL systems directly after the interview, and the Dictaphones immediately wiped. Electronic files will be identified by an ID number. Transcripts of each interview will be identified by an ID number, and participant identifiers will be kept in a separate document in a locked filing cabinet in a locked storage room in the Division of Psychiatry at UCL. The participant identifier document will be kept in a separate filing cabinet to the transcripts.

20 Workpackages 2.1 and 2.2

21 PATIENT AND PUBLIC INVOLVEMENT (PPI)

Patients and the public will be actively involved in this research programme and have been resourced appropriately to cover their planned roles. There are three key involvement mechanisms:

- Employment of a researcher who will draw on their lived experience of mental health problems within their role as a peer researcher. They will be a central member of the multi-disciplinary research team.
- We are building a Service User Research Group (SURG sometimes called Lived Experience Advisory Panel- LEAP) with six members including coverage of the sites selected. The McPin Foundation will convene and coordinate the SURG. The SURG will work closely with the peer researcher to deliver the case study work – planning data collection, directly promoting the study in the sites and being part of the synthesis phase as well as the overall study analysis phase integrating data from all work packages.

We will build a network of people and organisations to help us build a dissemination strategy including practitioners, carers and service users as well as organisations involved in the improvement of acute care services. This network will emerge through the contacts we build to deliver the research programme.

The lead coordinator of our involvement approach will be [name], research manager from McPin Foundation who is an expert in acute care and the Crisis Care Concordat.

22 FUNDING AND SUPPLY OF EQUIPMENT

The study funding has been reviewed by the UCL/UCLH Research Office, and deemed sufficient to cover the requirements of the study. NHS costs will be supported via UCLH and/or the Local Clinical Research Network.

The research costs for the study have been supported by the NIHR HS&DR programme grant 15/24/17.

23 PEER AND REGULATORY REVIEW

The study has been peer reviewed in accordance with the requirements outlined by UCL.

The Sponsor considers the procedure for obtaining funding from the NIHR to be of sufficient rigour and independence to be considered an adequate peer review.

24 ASSESMENT AND MANAGEMENT OF RISK

While many people find talking about their experiences to be helpful, some people may find that completing the questionnaire brings up issues that cause emotional distress. In this case the researcher will provide immediate emotional support to the participant, offer to pause or postpone the interview, and, if the participant asks, will contact a person of the participant's choice (e.g. current care coordinator, carer, friend, family member, colleague) for them.

If service users or carers report any untoward feedback, the researcher conducting the interview will confirm with the participant whether or not they would like the researcher to pass this on to the service or other relevant person. If the untoward feedback is of a nature that leads the researcher to be concerned for the safety of others, the participant will be informed that the feedback will be passed on to the relevant service or person to be addressed, but that if desired and possible they will remain anonymous.

In the event that the researcher feels concerned for their own safety they will be advised to bring the interview to an end. All face-to-face interviews will be conducted on NHS premises, and local safety policies and protocols should be adhered to by all researchers (e.g. informing local staff at the start of an interview, and again once the interview has been completed).

25 RECORDING AND REPORTING OF EVENTS AND INCIDENTS

15.1 Definitions of Adverse Events

Term	Definition	
Adverse Event (AE)	Any untoward medical occurrence in a patient or study participant, which does not necessarily have a causal relationship with the procedure involved.	
Serious Adverse Event (SAE).	 Any adverse event that: results in death, is life-threatening*, requires hospitalisation or prolongation of existing hospitalisation**, results in persistent or significant disability or incapacity, or consists of a congenital anomaly or birth defect 	

^{*}A life- threatening event, this refers to an event in which the participant was at risk of death at the time of the event; it does not refer to an event which hypothetically might have caused death if it were more severe.

25.2 **Assessments of Adverse Events**

Each adverse event will be assessed for severity, causality, seriousness and expectedness as described below.

15.2.1 Severity

Category	Definition
Mild	The adverse event does not interfere with the participant's daily routine, and does not require further procedure; it causes slight discomfort

20

^{**} Hospitalisation is defined as an in-patient admission, regardless of length of stay. Hospitalisation for pre-existing conditions, including elective procedures do not constitute an SAE.

Moderate	The adverse event interferes with some aspects of the participant's routine, or requires further procedure, but is not damaging to health; it causes moderate discomfort
Severe	The adverse event results in alteration, discomfort or disability which is clearly damaging to health

15.2.2 **Causality**

The assessment of relationship of adverse events to the procedure is a clinical decision based on all available information at the time of the completion of the case report form.

The differentiated causality assessments will be captured in the AE Log and SAE form.

The following categories will be used to define the causality of the adverse event:

Category	Definition
Definitely:	There is clear evidence to suggest a causal relationship, and other possible contributing factors can be ruled out.
Probably:	There is evidence to suggest a causal relationship, and the influence of other factors is unlikely
Possibly	There is some evidence to suggest a causal relationship (e.g. the event occurred within a reasonable time after administration of the study procedure). However, the influence of other factors may have contributed to the event (e.g. the participant's clinical condition, other concomitant events).
Unlikely	There is little evidence to suggest there is a causal relationship (e.g. the event did not occur within a reasonable time after administration of the study procedure). There is another reasonable explanation for the event (e.g. the participant's clinical condition).
Not related	There is no evidence of any causal relationship.
Not Assessable	Unable to assess on information available.

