- 3. Compare these characteristics to a cohort of people who receive acute crisis care without ADU input

STUDY DESIGN

This will be a cohort study. Five ADUs will be identified from the national survey carried out in WP1. We will invite people aged 18 and over who are consecutively admitted to each ADU to participate in baseline interviews and then telephone/internet follow-up 8-12 weeks after baseline, with administrative outcome data collected at 6 months.

We will invite people form the same crisis pathway to participate in the parallel non-ADU cohort. They must be receiving CRT home treatment when recruited, but could previously have been admitted to an inpatient ward during this episode.

We aim to recruit 80 people who receive ADU care and 80 people who do not, in the locality of each ADU chosen for the mixed-method case studies. This gives a total of 400 in each 'arm', and a combined total of 800.

STUDY SCHEDULE 5

At baseline, ADU staff will screen all service users consecutively admitted to their service from the start date. All service users who meet the inclusion criteria will be approached by ADU staff and asked if they are willing to be contacted by researchers to discuss participation further (except at sites where service users have already given consent to be contacted directly about research projects: in this circumstance, researchers will contact service users directly once their eligibility and any risk-related safety requirements have been established). The researchers will keep a record of potential participants to be contacted and the date and the name of the clinician with whom this was agreed. Researchers will ask the clinician who spoke to each service user to note the patient's agreement to be contacted by a researcher in their patient records. Those who agree will be contacted by a researcher with an information sheet and offer to answer any questions. Potential participants will be given at least 24 hours to consider whether they would like to take part, and then if still interested they will be consented by a researcher, who will also collect the baseline data.

Participants will be contacted by phone 8-12 weeks after baseline to be asked if they are willing to complete the questionnaire again. If so, the researcher will collect the data required from them. If a participant does not wish continue at follow up they are free to decline.

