7.1 Inclusion Criteria

Inclusion criteria are as follows:

- 18 years old or older
- Have used the ADU for at least one week
- Can read and understand English (or there are translation services in place to enable communication)
- Have capacity to provide informed consent
- Do not pose too high a risk to others or themselves to participate

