25.3 Recording adverse events

All adverse events will be recorded in the medical records in the first instance.

Procedures for recording and reporting Serious Adverse Events

All serious adverse events will be recorded in the medical records, and the study AE form, and the sponsor's AE log.

All SAEs (except those specified in section 16.5 as not requiring reporting to the Sponsor) must be recorded on a serious adverse event (SAE) form. The CI/PI or designated individual will complete an SAE form and the form will be preferably emailed to the Sponsor within 5 working days of becoming aware of the event. The Chief or Principal Investigator will respond to any SAE queries raised by the sponsor as soon as possible.

Where the event is unexpected and thought to be related to the procedure this must be reported by the Investigator to the Health Research Authority within 15 days.

[figure not shown]
Completed forms for unexpected SAES must be sent within 5 working days of becoming aware of the event to the Sponsor

Email forms to [contact]

[figure not shown]

Flow Chart for SAE reporting (this simple flow chart is for single site study, please amend in line with study specific requirements)

Reporting Urgent Safety Measures 25.6

If any urgent safety measures are taken the CI/ PI shall immediately and in any event no later than 3 days from the date the measures are taken, give written notice to the relevant REC and Sponsor of the measures taken and the circumstances giving rise to those measures.

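### The SAE footnote exempts hospitalisation for a pre-existing condition and makes no exception for an admission related to the study interview

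*Protocol*

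**What the plan says.** The table of definitions in section 25 (printed 15.1) lists five alternative SAE criteria. One is an event that "requires hospitalisation or prolongation of existing hospitalisation". Only this criterion carries the double-asterisk footnote. In the text as read from the PDF, the footnote appears within the severity table. It has two sentences: "Hospitalisation is defined as an in-patient admission, regardless of length of stay", and "Hospitalisation for pre-existing conditions, including elective procedures do not constitute an SAE".

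The population is defined by current crisis care. The inclusion criteria (7.1) require participants to "Have used the ADU for at least one week". The Study Design section says of the comparison cohort: "They must be receiving CRT home treatment when recruited, but could previously have been admitted to an inpatient ward during this episode".

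The study's contact with participants is by questionnaire and interview. The harm to participants that the protocol names is that "some people may find that completing the questionnaire brings up issues that cause emotional distress" (section 24, and in similar words under both recruitment sections).

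On related events, the section on recording and reporting SAEs (25.4 in the contents list) says: "Where the event is unexpected and thought to be related to the procedure this must be reported by the Investigator to the Health Research Authority", with a 15-day limit.

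**The concern.** The footnote gives elective procedures as something included in the exemption, so the exemption is not confined to planned admissions. It does not mention worsening, unplanned admission or relatedness to the study. In most study populations, such a clause removes a minor group of unrelated admissions. Here the exempted condition is the reason for recruitment, so the clause can apply to every psychiatric admission in either cohort.

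In people already in crisis, admission to a ward is an evident serious form of the distress the protocol names. If an interview contributed to one, the protocol's wording can remove it from the hospitalisation criterion. What is at stake is the safety record. A statement that no related SAEs occurred could then partly reflect the definition and not only what happened to participants.

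**Working it through.** The check is mainly a reading of the provisions against one another.

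**1. Is the event an adverse event?** Yes. The definition is "Any untoward medical occurrence in a patient or study participant, which does not necessarily have a causal relationship with the procedure involved". It does not exclude pre-existing illness.

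**2. Is it assessed?** Yes. Section 25.2 applies severity, causality, seriousness and expectedness assessments to each adverse event, not only to serious ones. The causality text says the result is captured in the AE Log and the SAE form.

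**3. Is it an SAE by hospitalisation?** An inpatient admission of any length counts, which would include a psychiatric ward. The footnote then takes out admissions for pre-existing conditions. All cohort participants are under ADU or crisis team care at recruitment, so an admission for the same illness is taken out on a literal reading, whatever its causality rating.

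**4. Is it an SAE by another criterion?** Only if it is fatal, life-threatening, disabling or a congenital anomaly. The footnote does not touch these four.

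**5. What depends on SAE status?** The reporting section requires SAEs to be entered in the medical records, the study AE form and the sponsor's AE log, and an SAE form to go to the sponsor within 5 working days. For other adverse events, section 25.3 requires only the medical records in the first instance. The causality text does not say whether its AE Log is the sponsor's, so it is not settled that a non-serious event reaches the sponsor.

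**6. Do the provisions agree?** Not fully. The causality category for possibly related events covers an event soon after the procedure to which the participant's clinical condition may also have contributed. The protocol thus foresees events that are both related to the procedure and influenced by existing illness. The footnote withholds SAE status from an admission of that kind. The SAE form rule also excepts events listed in a section 16.5. Section 16 is the qualitative study's eligibility section and has only 16.1 and 16.2, so that list cannot be consulted to resolve the point.

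**Background scale.** The inputs are 400 per cohort and the three planning rate pairs in Statistical Methods. The protocol's 310 per arm at 90% power is reproduced by the two-proportion formula with continuity correction, assuming two-sided 5% (310, 308 and 310 for the three pairs). Then 310 × 1.3 = 403, stated as 400. Expected participants readmitted to the acute pathway within 6 months = 400 × (rate without ADU + rate with ADU):

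- 400 × (0.40 + 0.274) = 269.6
- 400 × (0.45 + 0.320) = 308.0
- 400 × (0.50 + 0.368) = 347.2

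That is about 270 to 347 of 800. These are readmissions to the acute pathway from any cause. The protocol gives neither the share that are inpatient nor any share related to interviews.

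**The case against.** The strongest case for the footnote is that readmission is the primary outcome and is expected in roughly a third or more of participants (270/800 = 34%; 347/800 = 43%). Sending each one through SAE reporting would swamp the system with outcome events. The study is observational, its procedures are questionnaires and interviews, people who pose too high a risk are not eligible, and there is a procedure for distress. This justifies exempting unrelated readmissions. It does not explain why related ones are exempt too.

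An assessor may also treat an acute reaction to an interview as a new event and not as the pre-existing condition. That reading is open, but the footnote leaves it to individual judgement, so sites could report the same event differently.

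A reader might infer more than the protocol supports, in four ways:

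- **That an interview-provoked admission could never be an SAE.** An admission after a life-threatening act, for example, qualifies under another criterion.
- **That such an event escapes causality assessment, or survives only as a readmission in the outcome data.** Section 25.2 rates each adverse event, and it is entered in the medical records.
- **That the footnote keeps related admissions from the Health Research Authority.** The 15-day rule also requires the event to be unexpected, meaning not consistent with what the protocol says about the procedure. Questionnaire distress is described in the protocol, so an assessor could class the event as expected with or without the footnote.
- **That 270 to 347 measures the problem.** Those figures show only why some exemption is reasonable.

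**Conclusion.** The point holds in a narrow form. The footnote is a stated rule. Read literally, it removes SAE status, and the sponsor reporting tied to it, from a related psychiatric admission or prolonged stay that meets no other seriousness criterion. That fits poorly with the protocol's own causality categories and related-event rule.

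The conclusion rests on three assumptions: that the procedure in section 25 means the study questionnaire or interview, that a psychiatric readmission is read as being for the pre-existing condition, and that the footnote governs both admission and prolongation, since its marker follows both. The number of events affected cannot be derived from the protocol and is probably small. No analysis of readmission, satisfaction or cost is altered. The weight is modest, but the change is cheap and makes the safety record easier to interpret.

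**What to change.** Reconcile the footnote in section 25 with the causality categories in 25.2 and the related-event rule in the SAE reporting section. After reconciliation, the exemption should cover elective admissions and readmissions not judged related to the study procedure. Admissions or prolongations that the study team becomes aware of and judges related should stay within SAE reporting. The text should state which causality categories count as related, because the possibly related category is broad and the number of extra forms depends on it. The same amendment can correct or remove the reference to section 16.5.

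The cost is one footnote in a protocol amendment, a brief causality judgement by the existing CI/PI or designate, and what should be a small number of extra SAE forms. Section 25.2 already asks for a causality rating of each adverse event, so the judgement adds little to what is written. Unrelated readmissions, which form the primary outcome, stay exempt. Nothing in participants' care changes.
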